Q1	Quartile 1, 25th Percentile
Q3	Quartile 3, 75th Percentile
MedDRA	Medical Dictionary for Regulatory Activities
CTCAE	Common Terminology Criteria for Adverse Events

1. Introduction

The purpose of this statistical analysis plan (SAP) is to provide details of the statistical analyses that have been outlined within the protocol for Etanercept Phase 3b Study 20140339 dated 30 March 2017. The scope of this plan includes the final analysis that is planned and will be executed by the Biostatistics department.

2. Objectives

2.1 Primary

- To assess the injection site pain associated with a modified formulation of etanercept compared to the currently marketed etanercept in adult subjects with either rheumatoid arthritis (RA) or psoriatic arthritis (PsA) as measured by a visual analog scale (VAS)

2.2 Secondary

- To describe the injection site pain by disease indication

2.3 Safety

- To evaluate the safety of etanercept

3. Study Overview

3.1 Study Design

[figure not shown]
This is a phase 3b, multicenter, randomized, double-blind, 2-period, 2-sequence crossover study in subjects with RA or PsA who are naive to etanercept. The study will evaluate injection site pain associated with the current formulation of etanercept and the modified formulation of etanercept immediately after injection of each formulation.

Subjects will be randomized in a 1:1 ratio to receive each etanercept formulation in 1 of 2 crossover treatment sequences. Subjects randomized to the first treatment sequence (ie, sequence AB) will receive 1 dose of the current formulation (ie, treatment A) during the first study period, followed by a second visit 1 week later during the second study period at which time subjects will receive 1 dose of the modified formulation (ie, treatment B). Subjects randomized to the second treatment sequence will undergo the same procedures but will receive investigational product in the opposite order (ie, sequence BA). At each study visit subjects will inject the blinded treatment and immediately (ie, within 30 seconds of injection) record the associated injection site pain using the VAS. A total of 112 subjects will be enrolled with 56 subjects in each treatment sequence, stratified by disease indication (RA or PsA). A minimum of 20 PsA subjects will be enrolled, therefore enrollment of RA subjects will be limited to 92 subjects.

After study completion subjects may continue with modifiedly available etanercept. The study will consist of a screening period of up to 14 days, a treatment period of 2 weeks and a 30-day safety follow-up period.

3.1.1 Study Schema

The overall study design is described as follows:

[figure not shown]
Abbreviations: QW = every week

3.2 Sample Size

The primary objective of the study is to compare the injection site pain from the modified formulation of etanercept with that from the currently marketed formulation of etanercept.

The proposed sample size of 112 (ie, 56 per sequence treatment arm with at least 10 subjects with PsA) would provide approximately 53 subjects for each sequence treatment arm at the completion of the study, assuming an early termination or dropout rate of 5% for each sequence treatment arm over the course of the study. Subjects who drop out after the first injection will not be replaced by new subjects.

CCI

The sample population will be comprised of subjects with RA or PsA; the estimated injection site pain score for subjects with PsA is assumed to be similar to those with RA.

There are no data assessing injection site pain in subjects with either RA or PsA on any of the etanercept currently marketed or modified formulations. Given that RA subjects in non-etanercept studies have lower absolute injection site pain scores compared with healthy volunteers, the effect size between the formulations is expected to be smaller compared to that seen with healthy volunteers, in addition to expected attenuation at the second injection. Therefore, a conservative effect size of 8 mm was used for this study.

Therefore, the sample size of 53 per arm was calculated to have more than 90% power to detect a difference in means of 8 mm in the injection site pain score between the 2 formulations with corresponding SD of 25 using a 2-sided t-test (crossover analysis of variance) with a significance level of 0.05.

4. Study Endpoints and Covariates

4.1 Study Endpoints

4.1.1 Primary Endpoint

- Change in injection site pain score between the current formulation and the modified formulation as measured by the VAS

4.1.2 Safety Endpoint

- Adverse events

4.2 Planned Covariates and Subgroups

The disease indication will be adjusted as the straitification factor when analyzing the primary endpoint.

The following subgroup analyses will be performed to assess their influnce on the primary endpoint:

- Age (< 65, \geq 65)
- Sex (male, female)
- Baseline PGA (< median, \geq median)
- Baseline PGA (< 66.7 mm, \geq 66.7 mm)
- Prior biologic use (yes, no)
- Other subgroups may be evaluated as necessary

5. Hypotheses and/or Estimations

The primary hypothesis of this study is that the modified etanercept formulation will be associated with less injection site pain compared to the currently marketed etanercept formulation.

6. Definitions

Injection Site Pain Visual Analog Scale (VAS)

The injection site pain score is an assessment of the severity of the subject's injection site pain and will be completed by the subject immediately after the administration of the etanercept dose (ie, within 30 seconds) using a visual analog scale. The horizontal line is 100 mm in length with "0" and "No Pain At All" on the left end of the line and "100" and "Worst Pain Imaginable" on the right end of the line. This VAS has been specifically designed to capture injection site associated pain.

The 100 mm VAS is commonly used in such studies and has been shown to correlate well with categorical pain scales. A difference of 13 to 16 mm on the VAS is considered to be clinically meaningful (Gallagher et al, 2002) in a setting of acute pain.

Physician Global Assessment of Disease Activity (PGA)

The global assessment of the subject's overall RA or PsA disease activity will be assessed by the principal investigator or sub investigator for the study by completion of a VAS. The PGA will be completed -at screening, and on day 1 and day 8 before investigational product administration. The VAS is 100 mm in length with "0" and "No Activity at All" on the left end of the line and "100" and "Worst Activity Imaginable" at the right end of the line.

Enrollment

A subject is considered enrolled once randomized to treatment.

Randomization Date

The date the subject was assigned a randomization number.

Study Day 1

Study day 1 is defined as the first day of administration of investigational product after enrollment. The day prior to Study Day 1 is considered Day -1. For subjects that is not dosed, Study Day 1 is defined as the randomization date.

Study Day

Post-study day 1: study day = (date – date of Study Day 1) + 1

Pre-study day 1: study day = (date – date of Study Day 1)

End of Follow-up

When the last subject completes the last protocol-specified assessment in the study

End of Study (EOS)

When the last subject is assessed or receives an intervention for evaluation in the study (ie, last subject completes safety follow-up)

End of Study (primary completion)

When the last subject is assessed or receives an intervention for the purposes of final collection of data for the primary analysis (ie, last subject completes Study Visit 2)

Investigation Product

The term 'investigational product' is used in reference to etanercept, either the modified formulation or the modified formulation

Serious Adverse Event

A serious adverse event is defined as an adverse event that meets at least 1 of the following serious criteria: Serious Adverse Event (SAE)

- fatal
- life-threatening (places the subject at immediate risk of death)
- requires in-patient hospitalization or prolongation of existing hospitalization
- results in persistent or significant disability/incapacity
- congenital anomaly/birth defect
- other medically important serious event

An adverse event would meet the criterion of "requires in-patient hospitalization" if the event necessitated an in-patient admission to a health care facility. If an investigator considers an event to be clinically important, but it does not meet any of the serious criteria, the event could be classified as a serious adverse event under the criterion of "other medically important serious event." Examples of such events could include allergic bronchospasm, convulsions, blood dyscrasias, drug-induced liver injury (see [Appendix A](#) in protocol for drug-induced liver injury reporting criteria), or events that necessitate an emergency room visit, outpatient surgery, or urgent intervention. Since the criteria for the CTCAE grading scale differs from the regulatory criteria for serious adverse events, if adverse events correspond to grade 4 "life threatening" CTCAE grading scale criteria (eg, laboratory abnormality reported as grade 4 without manifestation of life threatening status), it will be left to the investigator's judgment to also report these abnormalities as serious adverse events. For any adverse event that applies to this situation, comprehensive documentation of the event's severity status must be recorded in the subject's medical record.

Treatment Emergent Adverse Event

A treatment-emergent adverse event is any adverse event that begins or worsens after the initial dose of investigational product and before the end of study. The severity of each adverse event will be graded using the CTCAE version 4.0 criteria, to be consistent with the version used for all etanercept studies. Adverse events will be coded using MedDRA (version 19.0 or later).

7. Analysis Subsets

7.1 Primary Analysis Set

The primary analysis set will include all subjects who received the dose of investigational product during each study period and who completed the injection site pain score during each study period. The primary endpoint will be evaluated using the primary analysis set.

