10.1.4 Handling of Missing and Incomplete Data

Subjects who dropout after the first injection will not be replaced by new subjects.

Subjects will be included in the safety analysis, but not in the efficacy analysis as described in [Section 10.1.2](#).

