10.5.2 Primary Efficacy Endpoint

As state above, analysis of covariance will be used to compare the difference in injection site pain score between subjects receiving etanercept in the current marketed formulation and in the modified formulation, with the disease indication (RA or PsA) and the treatment as factors, adjusting for period effect and sequence effect. Sensitivity analyses may be performed for the primary endpoint for subjects who complete the injection site pain score per protocol. In addition, the difference in injection site pain score will be evaluated by disease indication, using descriptive statistics.

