9.3 Handling of Missing and Incomplete Data

The following imputation for missing or incomplete data will be performed if required: Incomplete dates for adverse event and concomitant medication will be imputed as described in [Appendix A](#).

Subjects who drop out after the first injection will not be replaced by new subjects.

These subjects will be included in the safety analysis set, but not in the primary analysis set.

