10.1 General Principles

Descriptive statistics for continuous variables, consists of number of observations, mean, standard error and/or SD, median, 25th percentile (Q1), 75th percentile (Q3), minimum, maximum, and for categorical variables, the number of observations, frequency, and percentage will be presented. Subject disposition, demographics, baseline characteristics, and safety information will be summarized. There will be no adjustment for multiplicity and no imputation techniques for missing values. All analyses will be based on observed data.

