10.5 Primary Analyses

A mixed effects analysis of variance model will be used for the primary endpoint. Treatment, period, sequence and disease indication (RA or PsA) will be evaluated as fixed effects, and subject nested within sequence will be included as a random effect. The modified formulation of etanercept will be used as the test treatment and current formulation of etanercept as the reference treatment.

The null hypothesis that there is no difference of injection site pain between the current and modified formulation will be tested and p-value will be provided. The least square mean of the injection site pain score and the difference between the formulations will be estimated and the corresponding 2-sided 95% CI will be provided..

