10.6 Other Analyses

The descriptive statistics will be provided for the injection site pain score for overall and by indication and formulation.

Sensitivity analyses will be performed for the primary endpoint for subjects in the primary analysis set, excluding the subject(s) with injection(s) administrated without warming the investigation product to the required temperature.

Subgroup analyzes will be conducted for the primary endpoint with the subgroups defined in [Section 4.2](#).

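### Does leaving subjects with only one pain score out of every planned estimate of the treatment difference put the result at risk?

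*SAP*

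**What the plan says.** The rule appears in both documents. SAP 7.1 and Protocol 10.1.2 restrict the primary analysis set to subjects "who received the dose of investigational product during each study period and who completed the injection site pain score during each study period". On subjects who leave after the first injection, SAP 9.3 states: "These subjects will be included in the safety analysis set, but not in the primary analysis set". Protocol 10.1.4 agrees: "Subjects will be included in the safety analysis, but not in the efficacy analysis as described in" Section 10.1.2.

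Four other provisions bear on the point:

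- **Model (SAP 10.5):** treatment, period, sequence and indication are fixed effects, and "subject nested within sequence will be included as a random effect".
- **Missing data (SAP 10.1):** scores are not imputed, and "All analyses will be based on observed data".
- **Sensitivity analyses:** SAP 10.6 begins "Sensitivity analyses will be performed for the primary endpoint for subjects in the primary analysis set" and then removes subjects whose product was not warmed, so it can only shrink the set. Protocol 10.5.2 is optional: "Sensitivity analyses may be performed for the primary endpoint for subjects who complete the injection site pain score per protocol". It does not say whether both scores are needed.
- **Description and listings:** SAP 10.6 adds "The descriptive statistics will be provided for the injection site pain score for overall and by indication and formulation" and names no analysis set. SAP 10.2 reports the timing and reason of each withdrawal and the reason for each exclusion from an analysis set. SAP 10.7.5 lists formulation and period for each administration.

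**The concern.** Whether a subject has two scores is known only after randomisation, and it could depend on how much the first injection hurt. In sequence AB the first injection is the current formulation, which is expected to hurt more. Pain-driven loss would then be heavier in AB than in BA, and the two groups of completers would no longer be fully comparable. That could distort the one comparison the trial is built on.

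The plan also seems to have the remedy at hand. A model with a random subject effect accepts a single score without imputation, yet no visible text fits it to subjects with one score. The only firm sensitivity analysis goes the other way and excludes more subjects. A reader could reasonably ask whether the excluded scores would move the estimate.

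**Working it through.** **Inputs.** From SAP 3.2: 56 enrolled and 53 completing per sequence, 5% dropout, difference 8 mm, SD 25, 2-sided 0.05. The correlation ρ between a subject's two scores and the cause of dropout are not visible (the sample-size sections contain redactions), so both are assumed and varied.

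**1. The planned figure.** Read SD 25 as the SD of the within-subject difference. Then SE = 25/√106 = 2.43 mm, the noncentrality is 8/2.43 = 3.29, and with 104 degrees of freedom the power is 0.904. With 52 per sequence it is 0.898, so 53 is the smallest number above 90%. Since 56 × 0.95 = 53.2, the loss of one-score subjects is already in the enrolment target.

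**2. Subjects affected.** 112 × 0.05 = 5.6, about 6.

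**3. How far their scores can move the estimate.** Let p be the share of a sequence with only a period-1 score, and d their mean period-1 score minus that of the completers. Fitting the SAP 10.5 model to all observed scores moves the period-1 minus period-2 difference of that sequence by (1 − ρ)·p·d. The formulation contrast has opposite signs in the two sequences, so

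all-observed − completers (current minus modified) = (1 − ρ)/2 × (p_AB·d_AB − p_BA·d_BA).

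With 6 such subjects:

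| Split AB/BA | d | p_AB·d_AB − p_BA·d_BA | ρ = 0.3 | ρ = 0.5 | ρ = 0.7 |
|---|---|---|---|---|---|
| 3/3 | 20 mm | 0 | 0.00 | 0.00 | 0.00 |
| 4/2 | 20 mm | (2/56) × 20 = 0.71 | 0.25 | 0.18 | 0.11 |
| 6/0 | 20 mm | (6/56) × 20 = 2.14 | 0.75 | 0.54 | 0.32 |
| 6/0 | 40 mm | (6/56) × 40 = 4.29 | 1.50 | 1.07 | 0.64 |

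Even with all six in one sequence and 40 mm above the completers, the shift (in mm) is below one standard error.

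**4. Bias of the completers' estimate if period-1 pain drives dropout.** Simulated crossover trials, normal scores, true difference 8 mm, 5% dropout overall; shortfall toward zero in mm:

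| Mechanism | ρ = 0.3 | ρ = 0.5 | ρ = 0.7 |
|---|---|---|---|
| Gradual (odds × 2.7 per SD of pain) | 0.12 | 0.08 | 0.05 |
| Steep (odds × 7.4 per SD) | 0.28 | 0.19 | 0.13 |
| Extreme (all above a cut-off leave) | 0.51 | 0.38 | 0.23 |

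Hand check of the extreme case at ρ = 0.5. Each score has SD 25/√(2 × 0.5) = 25, and the cut-off removes 6.6% of AB and 3.4% of BA. Truncating a normal distribution lowers the completers' mean by 25·φ(z)/(1 − p): 25 × 0.128/0.934 = 3.43 in AB (z = 1.51) and 25 × 0.0755/0.966 = 1.95 in BA (z = 1.82). The bias is 0.25 × (3.43 − 1.95) = 0.37 mm, in line with the simulation. With no true difference and the same dropout rule, the two terms are equal and the bias is zero. Type I error stays at 0.049 to 0.053.

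Power of the completers' analysis is 0.899 to 0.902 (gradual) and 0.884 to 0.896 (extreme), against 0.904 to 0.910 with all scores. At 10% dropout the shortfall is 0.08 to 0.21 mm (gradual) and 0.36 to 0.79 mm (extreme). Clipping the scores to the 0 to 100 scale, with assumed means of 20 to 30 mm, gave shortfalls of 0.10 to 0.57 mm at 5% dropout.

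**5. Precision gained by adding the single scores.** With 3 per sequence and per-score variance s² = 625/[2(1 − ρ)], the variance is ½ × [(1 − ρ)²s²/56 + (1 − ρ²)s²/53]. At ρ = 0.5: ½ × (2.79 + 8.84) = 5.82, so SE = 2.412 mm against 2.428. For ρ from 0.25 to 0.75 the SE is 2.404 to 2.420 mm, a reduction of 1.0% to 0.3%.

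**6. The reverse case.** Suppose the most pain-prone subjects leave, 7% of AB and 3% of BA. A subject's general pain level cancels in the within-subject difference, so the completers' estimate is unbiased. The all-observed fit overstates the benefit by 0.32 to 0.35 mm.

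**The case for a change.** The strongest case for the concern has four parts. No visible text plans a modelled difference that uses the single scores, and SAP 9.4 (detection of bias) looks only at protocol deviations. Protocol 2.3 itself links injection pain to poor compliance, so loss after a painful first injection is a fair question. Protocol 8.1 says that data up to withdrawal of consent will be included in the analysis. And an extra run of the SAP 10.5 model needs no new data.

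The factual observation stands, limited to a modelled difference: means by formulation on all observed scores are not ruled out by SAP 10.6, and Protocol 10.5.2 leaves its set open. The rest does not make a defect:

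- The remark on compliance does not show that pain drives dropout here, over two injections about a week apart in candidates for sustained etanercept. A score can also be missing for other reasons, such as a skipped dose.
- Withdrawn subjects' data do enter the safety analysis. Protocol 10.1.4 excludes these subjects from efficacy as a stated choice.
- An extra fit could hardly diagnose the problem. It disagrees with the completers' analysis on significance in 1.5% to 2.6% of trials under gradual pain-driven dropout, but already in 1.3% to 1.8% under purely random dropout. Only the extreme cut-off reaches 2.7% to 4.5%.
- It assumes missingness at random. Where that fails as in step 6, it errs in favour of the modified formulation, while the planned analysis errs against it or not at all.

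**Conclusion.** The concern does not hold. The completers' rule is deliberate, identical in both documents, suited to a within-subject endpoint and already covered by the sample size. At 5% dropout its plausible cost is about 0.05 to 0.5 mm toward zero, against a standard error of about 2.4 mm, with type I error intact. The cost in power is within about 2.5 percentage points even under the extreme mechanism (0.884 against 0.908 at ρ = 0.3). Adding the single scores would change neither the sample size nor, in all but a few trials, the conclusion. It replaces one unverified dropout assumption with another. SAP 10.2 and 10.7.5 already show who was excluded, why and after which formulation, so a further analysis would be a matter of taste.

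This rests on a true difference of 8 mm, SD 25 as the SD of the within-subject difference, a correlation of about 0.25 to 0.75, dropout near 5% and the mechanisms tried. The code in SAP Appendix C is redacted and could not be checked.

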7.2 Safety Analysis Set

The safety analysis set will include all subjects who received at least 1 dose of investigational product during the study. All safety endpoints will be evaluated using the safety analysis set.

8. Interim Analysis and Early Stopping Guidelines

No interim analysis is planned for this study.

9. Data Screening and Acceptance

9.1 General Principles

The objective of the data screening is to assess the quantity, quality, and statistical characteristics of the data relative to the requirements of the planned analyses.

9.2 Data Handling and Electronic Transfer of Data

The Amgen Global Study Operations-Data Management (GSO-DM) department will provide all data to be used in the planned analyses. This study will use the RAVE database.

9.3 Handling of Missing and Incomplete Data

The following imputation for missing or incomplete data will be performed if required: Incomplete dates for adverse event and concomitant medication will be imputed as described in [Appendix A](#).

Subjects who drop out after the first injection will not be replaced by new subjects.

These subjects will be included in the safety analysis set, but not in the primary analysis set.

9.4 Detection of Bias

Lack of protocol compliance and the potential for biased statistical analyses will be examined by assessing the incidence of important protocol deviations in each treatment group. The clinical study team will identify and document the criteria for important protocol deviations.

9.5 Outliers

Outlier data will not be excluded, unless for any specific reason(s) that could be justified.

9.6 Distributional Characteristics

Where appropriate, the assumptions underlying the proposed statistical methodologies will be assessed. If required data transformations or alternative non-parametric methods of analyses will be utilized.

